4.2 Registration Process

Before an institution may begin participation in a M.D. Anderson protocol, all the required steps outlined in [Section 3.3 of Appendix K](#) concerning regulatory documents, must be fulfilled.

Prior to protocol enrollment and initiation of treatment, subjects must sign and date an Institutional Review Board (IRB) approved consent form. Patients at participating institutions should be registered with their institutional central registration first, following each institution's established policies. All patients must then be registered in the M.D. Anderson database, Clinical Oncology Research System (CORe) before beginning treatment. CORe is a clinical research information management system supporting clinical research trials at U.T. M.D. Anderson Cancer Center and collaborative sites across the nation.

At the time of registration, the registrant will be requested to verify the patient's eligibility in

CORE by answering a series of inclusion/exclusion protocol questions and the name of the registering physician. Once patient eligibility has been established, the patient will then be automatically registered and randomized to the appropriate treatment arm. Therapy may then be initiated per protocol guidelines.

Please see [Section 3.3 of Appendix K](#) for registration requirements and data collection guidelines.

5. TREATMENT PLAN

5.1 Agent Administration

Patients will be randomized 2:1 to one of two treatment arms (i.e. Arm A: MK-2206; Arm B: Everolimus). Treatment will be administered on an outpatient basis. Reported adverse events and potential risks for MK-2206 and everolimus are described in [Section 7](#). Appropriate dose modifications for MK-2206 and everolimus are described in [Section 6](#). No investigational or commercial agents or therapies other than those described below may be administered with the intent to treat the patient's malignancy.

The patient will be requested to maintain a medication diary of each dose of medication. The medication diary will be returned to clinic staff at the end of each course. Patients should be instructed to record doses as they take them and not to enter them in batches at a later time.

5.1.1 MK-2206 (Arm A)

There is no specific guidance available regarding overdose due to the lack of clinical experience. In case of an acute overdose, it is recommended that activated charcoal be administered orally to reduce the absorption of MK-2206.

MK-2206 is an oral drug that may be administered once weekly (QW). Patients should take MK-2206 at a starting dose of 200mg PO once weekly 2 hours before or after a meal. The phase 1 clinical pharmacology study of MK-2206 in volunteers included a panel of 8 patients who were administered MK-2206 after a high-fat breakfast. The results indicated a moderate increase in AUC and a slight increase in Cmax relative to that of fasted patients.

A study cycle will be 4 weeks in length. Patients who are progression free after 1 year may be given a 12 week (+/- 7 days) study drug supply.

5.1.2 Everolimus (Arm B)

Everolimus is an oral drug that will be administered once daily. Patients should take everolimus at a starting dose of 10 mg orally once daily. Patients will be instructed to take everolimus in the morning, at the same time each day.

A study cycle will be 4 weeks in length.

5.2 Screening and Evaluation On-Study

Within four weeks of study entry:

- All the participants must have signed a consent form agreeing to participate in the study.
- Radiological studies shall include a chest X-ray, and CT scans of the chest and abdomen for the baseline tumor measurement, a CT or MRI of the brain, and a bone scan. Appropriate additional studies should be obtained to fully define the extent and severity of existing or suspected malignant disease.
- A MRI of the spine should be obtained, if there is suspicion of evolving cord or nerve root compression. Spinal cord or nerve root compression syndromes should be managed before trial entry.
- A skeletal survey and a CT scan of the pelvis will be ordered as clinically indicated.
- A 12-lead electrocardiogram

Within two weeks of study entry:

- All patients must undergo a complete history and physical examination, including vital signs, ECOG performance status, recent weight loss, height, and current weight.
- Concurrent non-malignant disease and medical therapy must be documented. On-study forms must be filled out completely.
- All prior anti-cancer treatment must be recorded in proper detail. Any residual toxicity from prior therapies should be recorded by using the grading schema in NCI Common Toxicity Criteria v4.0.
- Patient's MSKCC prognostic criteria will be recorded. ([Appendix J](#)).
- Laboratory studies shall include CBC w/differential, platelet count, chemistry panel (total protein, albumin, alkaline phosphatase, AST and/or ALT, calcium, LDH, total bilirubin, BUN, creatinine, phosphorus, uric acid, sodium, potassium, chloride, carbon dioxide, magnesium, glucose), amylase, lipase, PT and PTT, and urinalysis (pH, specific gravity, ketones, RBC, WBC, bilirubin, and protein). T4, TSH will be obtained. Hemoglobin A1C, fasting glucose, lipid panel and triglycerides will be obtained. Serum pregnancy test in female patients of childbearing potential will also be included and must be negative within 24 hours of enrolling on this study.

Optional studies with patient consent:

- Nephrectomy blocks will be acquired to: a) generate tissue microarray (TMA) to stain for PI3K pathway components and other biologically relevant pathways and molecules and b) perform virtual karyotyping.
- Baseline blood will be drawn for a) plasma and serum analysis of cytokines and angiogenesis factors b) circulating monocytic cells.

Evaluation During Treatment:

On-study evaluations will consist of the following study activities every four weeks +/- four days (Patients who are progression free after 1 year may have the following performed every 12 weeks +/- 7days):

- History and physical exam by physician, or mid-level provider at each scheduled visit.
- Vital signs (including weight) and ECOG performance status
- Serum chemistry including total protein, albumin, alkaline phosphatase, AST and/or ALT, calcium, LDH, total bilirubin, BUN, creatinine, phosphorus, uric acid, sodium, potassium, chloride, carbon dioxide, magnesium, and glucose at each scheduled visit (+/- 4 days). Hematology including CBC with differential and platelet counts and PT and PTT at each scheduled visit (+/- 4 days). T4, TSH, will be obtained at each scheduled visit (+/- 4 days). Amylase and lipase will be repeated at each scheduled visit as clinically indicated. Fasting lipid panel and glucose will be done every 4 weeks for the first 8 weeks and every 8 weeks thereafter. Cycle 1 Day 1 blood tests will not be done if screening labs were done in the previous 7 days.
- Serum glucose level monitoring for patients every 7 days +/- 2 days for patients on MK2206 during the first cycle of therapy. These measurements do not have to be performed at the study site, but data must be provided to the study team by the patient.
- Hemoglobin A1c levels need to be monitored at the beginning of each cycle for patients on MK2206 who require antihyperglycemic medication.
- Record concomitant medications at each scheduled visit.
- Monitor for adverse events. Treatment-related toxicity (acute and cumulative) will be performed every scheduled visit.
- On C1D1 only, patients randomized to MK-2206 will have an ECG within 4 hours of taking study drug.

Optional studies with patient consent:

- Blood will be drawn for a) plasma and serum analysis of cytokines and angiogenesis factors and b) circulating monocytic cells.

In addition to the above, the following will be performed every eight weeks +/- 7 days (Patients who are progression free after 1 year may have the following performed every 12 weeks +/- 7days):

- Repeat radiologic studies (CT, MRI, Chest x-ray and bone scan as indicated) to evaluate disease progression or response (in accordance with restaging of disease). Studies to confirm a complete response or document progressive disease will be performed as needed.
- 12-lead electrocardiogram (ECG)

End of Treatment

The following study activities will be completed after treatment has been discontinued for any reason:

- Physical exam.
- Vital Signs including weight
- Radiologic assessment and assessment of response.
- 12-lead electrocardiogram.
- Urinalysis to include: pH, specific gravity, ketones, RBC, WBC, bilirubin, protein, and glucose.
- Serum chemistry including total protein, albumin, alkaline phosphatase, AST and/or ALT, calcium, LDH, total bilirubin, BUN, creatinine, phosphorus, uric acid, sodium, potassium, chloride, carbon dioxide, magnesium, and glucose
- TSH, T4.
- Hematology to include: CBC with differential and platelet count, PT and PTT.
- Record for concomitant medications.
- Monitor for adverse events.

Optional studies with patient consent:

- Blood will be drawn for a) plasma and serum analysis of cytokines and angiogenesis factors b) circulating monocytic cells

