6.1 MK-2206

| Dose Level | MK2206 Dose |
|-------------------|------------------|
| -2 | 90 mg PO weekly |
| -1 | 135 mg PO weekly |
| 0 (starting dose) | 200 mg PO weekly |

Clinically significant Grade 3 side effects attributable to MK2206 will require dose withholding until grade 1 levels of toxicity are reached. At that point drug can be restarted at the next lower dose level. If after four weeks the toxicity remains completely controlled, dose re-escalation can be attempted at the treating physician's discretion.

If toxicity does not resolve to a grade 1 or lower levels within four weeks of drug discontinuation, the patient will be taken off study.

Clinically significant Grade 4 side effects attributable to MK2206 which are considered medically relevant will result in patient being taken off study.

Management of Hyperglycemia

Grade 3 hyperglycemic events (>250 mg/dL) should lead to consultation with an endocrinologist or other specialist. If glucose levels do not return to grade 1 or lower within one week of appropriate therapy, patients should be considered to have a DLT.

Appropriate therapy will usually involve oral antihyperglycemic agents, since the inhibition of glucose transport into the cell by AKT/mTOR inhibitors may render insulin ineffective. The goal of therapy is to keep fasting glucose <150 mg/dL, random blood glucose levels <180 mg/dL, and Hemoglobin A1c <8%. Glucose monitoring should be performed weekly, during the first cycle of therapy, and on day 1 of subsequent cycles, prior to drug administration.

Hemoglobin A1c monitoring, for patients requiring treatment of hyperglycemia, should be

performed with each cycle of MK-2206 therapy.

Management of Rash

Patients who develop grade 3 rash will have treatment withheld as outlined above. For patients with persistent grade 2 rash that does not respond to conservative measures, and which in the opinion of the treating physician is significantly compromising quality of life, dose can be held, and once rash reaches grade 1 intensity or lower, MK2206 can be restarted at the same dose level. If a second dose withholding is required for redevelopment of persistent refractory grade 2 rash, dose can be withheld and then restarted at one dose level lower once rash reaches a grade 1 or lower level. MK2206 re-escalation can be attempted after 4 weeks if in the judgment of the treating physician the patient's side effect profile warrants re-escalation.

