4. Antifungal agents must be avoided unless a fungal infection is diagnosed. In particular, systemic imidazole antifungal agents (ketoconazole, fluconazole, itraconazole, etc.) should be avoided in all patients due to their strong inhibition of metabolism of study drugs, thereby leading to higher drug level exposures. Therefore, topical antifungal agents are preferred if an infection is diagnosed. Similarly, antiviral agents such as acyclovir should be avoided unless a viral infection is diagnosed. Note: Stomatitis/oral mucositis should be appropriately graded using the functional grading given on the NCI-CTC for adverse events, version 4.0.

Management of hyperlipidemia and hyperglycemia

Treatment of hyperlipidemia should take into account the pre-treatment status and dietary habits. Blood tests to monitor hyperlipidemia must be taken in the fasting state. Grade 2 hypercholesterolemia (> 300 mg/dL or 7.75 mmol/L) or Grade 2 hypertriglyceridemia (>2.5 x ULN) should be treated with a 3-hydroxy-3-methyl-glutaryl (HMG)-CoA reductase inhibitor (e.g., atorvastatin, pravastatin) or appropriate lipid-lowering medication, in addition to diet. Patients should be monitored clinically and through serum biochemistry for the development of rhabdomyolysis and other adverse events as required in the product label/data sheets for HMG-CoA reductase inhibitors.

Note: Concomitant therapy with fibrates and an HMG-CoA reductase inhibitor is associated with an increased risk of a rare but serious skeletal muscle toxicity manifested by rhabdomyolysis, markedly elevated creatine kinase (CPK) levels and myoglobinuria, acute renal failure and sometimes death. The risk versus benefit of using this therapy should be determined for individual patients based on their risk of cardiovascular complications of hyperlipidemia.

Grade 3 **hyperglycemia** has been observed in patients receiving everolimus therapy. It is suggested that optimal glucose control should be achieved before starting a patient on everolimus and should be monitored during everolimus therapy.

Table 5 - Management of non-infectious pneumonitis

| Worst Grade Pneumonitis | Required Investigations | Management of Pneumonitis | Everolimus Dose Adjustment |
|-------------------------|---|---|--|

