10. STUDY CALENDAR

Baseline evaluations are to be conducted within 2 week prior to start of protocol therapy. Scans and x-rays must be done ≤ 4 weeks prior to the start of therapy. In the event that the patient's condition is deteriorating, laboratory evaluations should be repeated within 48 hours prior to initiation of the next cycle of therapy.

| | Screening | Every 4 weeks ^k | Every 8 Weeks ^k | Early Withdrawal/ End of Study |
|---|-------------------|----------------------------|----------------------------|-----------------------------------|
| Informed consent | x ^a | | | |
| Medical history | x ^b | x | | |
| Physical exam | x ^b | x | | x |
| Vital signs | x ^b | x | | x |
| Performance status | x ^b | x | | |
| Weight | x ^b | x | | x |
| Height | x ^b | | | |
| Concurrent meds | x ^b | x | | x |
| CBC w/diff, plts | x ^b | x | | x |
| Serum chemistry | x ^{b, e} | x ^{e, f} | | x |
| HGB A1C | x ^b | | | |
| Fasting Glucose, Fasting Lipid Panel, and triglycerides | x ^b | x ⁱ | x ⁱ | |
| B-HCG | x ^{b, c} | | | |
| PT/PTT | x ^b | x | | x |
| T4, TSH | x ^b | x | | x |
| Amylase, Lipase | x ^b | x ^h | | |
| Hemoglobin A1C | | x ^g | | |
| Urinalysis | x ^b | x | | x |
| EKG | x ^a | x ^j | x | x |
| Adverse event evaluation | <-----> | | | |
| Chest X-Ray | x ^a | | x | x |
| CT Scan Chest/Abdomen | x ^a | | x | x |

| | | | | |
|-------------------------------------|-------------------|---|---|---|
| MRI or CT of Brain | x ^a | | x | x |
| Bone Scan | x ^a | | x | x |
| Other Radiological Scans | x ^{a, d} | | x | x |
| Optional Correlative Blood | x | x | | x |
| Optional Archived Tissue Collection | x | | | |

a Within 4 weeks of study entry

b Within 2 weeks of study entry

c Within 24 hours of study entry

d MRI spine should be obtained if suspicion of evolving cored or nerve root compression. A skeletal survey and/or a CT scan of the pelvis will be ordered as clinically indicated.

e Serum chemistry will include total protein, albumin, alkaline phosphatase, AST and/or ALT, calcium, LDH, total bilirubin, BUN, creatinine, phosphorus, uric acid, sodium, potassium, chloride, carbon dioxide, glucose, and magnesium.

f Serum glucose testing will be done every 7 days for the first cycle of treatment for those patients receiving MK-2206. This can be done at a local physician's office.

g Only for patients on MK-2206 who require anti-hyperglycemic medication.

h Repeated only if indicated

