i Fasting glucose and lipid panel will be done every 4 weeks for the first 8 weeks and every 8 weeks thereafter.

j Course 1 Day 1 post-treatment (only for patients randomized to MK-2206).

k Patients who are progression free after 1 year may have the following performed every 12 weeks +/- 7days

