13.4 Statistical Analysis Plan

The primary endpoint, progression-free survival (PFS), is defined as the time interval between date of treatment and date of disease progression, date of death or last follow-up date, whichever occurred first. The probability of PFS be estimated using the Kaplan-Meier method and will be compared between the two treatment arms using stratified log-rank test. Patients' safety data will be summarized by treatment arm, category, severity and relevance.

For secondary analyses, the Kaplan-Meier method will be used to estimate overall survival (OS) and time to failure (TTF), and stratified log-rank test will be used to compare between the two treatment arms. The OS is defined as the time interval between the date of treatment and the date of death or last follow-up, whichever occurred first. The TTF is defined as the time interval between the date of treatment and the date of disease progression, date of death, date of treatment discontinuation due to severe toxicity or last follow-up date, whichever occurred first. Overall response (OR) is defined as CR+PR and logistic regression model will be fit to assess the effect of treatment on the rate of OR.

Since the correlative studies being performed are by nature exploratory, and have not been

performed before in patients with RCC receiving mTOR inhibitors or AKT inhibitors, powering of these endpoints is not possible. Clinical benefit is defined as CR+PR+SD and again, we will fit logistic regression models to assess the effects of treatment, AKT activation, circulating cytokines and angiogenic factors, and karyotype on clinical benefit. The interaction effect between treatment and these exploratory factors will also be evaluated.

For virtual karyotyping, technique specific statistical analyses are outlined in [Appendix G](#).

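### Weekly cycle-1 glucose testing on MK-2206 only makes the by-arm safety summary likely to record more hyperglycemia on MK-2206, even if the true risk were equal

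*Combined protocol and SAP*

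**What the plan says.** Three places set the extra testing, all for MK-2206 alone:

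- Section 5.2: "Serum glucose level monitoring for patients every 7 days +/- 2 days for patients on MK2206 during the first cycle of therapy". It adds: "These measurements do not have to be performed at the study site, but data must be provided to the study team by the patient".
- Section 10, calendar footnote f: "Serum glucose testing will be done every 7 days for the first cycle of treatment for those patients receiving MK-2206".
- Section 6.1: "Glucose monitoring should be performed weekly, during the first cycle of therapy, and on day 1 of subsequent cycles, prior to drug administration".

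None of the three says whether the weekly sample is fasting.

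Both arms share two further glucose measurements. One is the chemistry panel at each 4-weekly visit (section 5.2), which includes glucose and is not labelled fasting. The other is a labelled fasting test (section 10, footnote i): "Fasting glucose and lipid panel will be done every 4 weeks for the first 8 weeks and every 8 weeks thereafter".

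For the comparator, section 6.2 says that grade 3 hyperglycemia "has been observed in patients receiving everolimus therapy" and that glucose should be monitored on everolimus, but it gives no frequency.

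Section 7.4 requires every adverse event to be reported. Section 13.4 says that "safety data will be summarized by treatment arm, category, severity and relevance" and does not mention that the arms are tested at different rates.

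**The concern.** An arm that is tested more often will, other things equal, have more abnormal values found. Here the difference falls in the first four weeks and on a toxicity that both drugs cause. Section 2.2 (Clinical Toxicology) describes the MK-2206 episodes as mostly mild and transient. That is the kind of event extra looks find and a single week-4 look misses.

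Events found by the extra tests enter the routine safety data, so the by-arm hyperglycemia row mixes drug effect with testing intensity. The risk lists in section 7.1 already put hyperglycemia in the more-than-20% category for MK-2206 and the 20%-or-less category for everolimus. A reader could take an excess in the trial as confirmation, when the planned table cannot separate a true excess from extra testing. MK-2206 safety is listed among the primary objectives in section 1.1, although section 13.1 lists safety as a secondary endpoint.

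Fasting status adds a smaller difficulty. Section 2.3.5 asks that it be verified when glucose is interpreted, and section 6.1 sets different goals for fasting (below 150 mg/dL) and random (below 180 mg/dL) values. The extra MK-2206 results arrive without that label.

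**Working it through.** The plan states no hyperglycemia rate or between-arm difference, so there is no figure to reproduce. The check asks what the arms would record if the true risk were equal.

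**Looks after day 1 (sections 5.2, 6.1 and 10).** A chemistry and a fasting glucose due at the same visit count as one look.

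- By day 29: MK-2206 on days 8, 15, 22 and 29 = 4; everolimus on day 29 = 1.
- By week 20: the shared visits at weeks 4, 8, 12, 16 and 20 = 5; MK-2206 has 5 + 3 = 8.

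**Repeated-test model.** Let p be the chance of a raised value per test and k the number of looks.

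- Independent tests: detection = 1 - (1 - p)^k.
- Correlated tests: detection = 1 - E[Φ((t - √ρ·z)/√(1 - ρ))^k], with t = Φ⁻¹(1 - p), z standard normal and ρ the within-patient correlation. At ρ = 1 detection equals p whatever k is.

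The values of p (0.05 to 0.20) and ρ (0 to 1) are assumptions; the documents give neither. For p = 0.10 with independent tests, day 29 gives 1 - 0.9^4 = 34.4% against 10.0%, a ratio of 3.44. Week 20 gives 1 - 0.9^8 = 57.0% against 1 - 0.9^5 = 41.0%, a ratio of 1.39.

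Detected, MK-2206 vs everolimus (ratio):

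| ρ | p | Day 29 (4 vs 1) | Week 20 (8 vs 5) |
|---|---|---|---|
| 0 | 0.05 | 18.5% vs 5.0% (3.71) | 33.7% vs 22.6% (1.49) |
| 0 | 0.10 | 34.4% vs 10.0% (3.44) | 57.0% vs 41.0% (1.39) |
| 0 | 0.20 | 59.0% vs 20.0% (2.95) | 83.2% vs 67.2% (1.24) |
| 0.5 | 0.10 | 25.9% vs 10.0% (2.59) | 36.7% vs 29.2% (1.26) |
| 0.9 | 0.10 | 16.3% vs 10.0% (1.63) | 19.5% vs 17.4% (1.12) |
| 1 | 0.10 | 10.0% vs 10.0% (1.00) | 10.0% vs 10.0% (1.00) |

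**Would the excess be seen?** With 70 and 35 patients (section 13.2), p = 0.10 and binomial sampling, the chance that the observed MK-2206 rate is the higher one by week 20 is 0.93, 0.76, 0.58 and 0.47 for ρ = 0, 0.5, 0.9 and 1.

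**Episode model.** Let one episode start uniformly over days 1 to 29 and last D days (assumed). For D up to 28, everolimus detection at day 29 is D/28. For D up to 7, MK-2206 detection is 4D/28; for longer episodes it is 100%.

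- D = 3: 12/28 = 43% vs 3/28 = 11%.
- D = 7: 100% vs 25%.
- D = 14: 100% vs 50%.
- D = 21: 100% vs 75%.
- D = 28 or more: 100% vs 100%.

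**On the common schedule only**, k is the same in both arms, so the expected ratio under equal true risk is 1.0 in the repeated-test model.

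**The case against.** The strongest reply is that the effect is uncertain, fades with time and decides nothing. Much of that stands.

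- A reader might infer that the table is bound to show an excess, or a three- to fourfold one. The documents do not support either. The large ratios need independent tests, assumed per-test rates and a cycle-1 window, whereas section 13.4 does not tabulate by cycle. By week 20 (20 × 7/30.4 = 4.6 months, close to the assumed 4.9-month everolimus median PFS) the ratio is at most about 1.5. If episodes last about four weeks or longer, the excess vanishes.
- The assumed 5-20% has no source in the plan. Section 2.2 reports hyperglycemia in about 76% of patients on every-other-day dosing. If that came from four independent tests, p would be 1 - 0.24^(1/4) = 0.30 and the day-29 ratio 0.76/0.30 = 2.5. The description of episodes as transient comes from the same experience, gives no duration, and this trial doses weekly.
- Equal true risk is a hypothetical. Given the risk lists in section 7.1, an observed excess should not be presumed an artefact.
- No between-arm safety test is planned. The stopping rule in section 13.1 covers MK-2206 alone and counts only grade 3 or worse toxicity that ends treatment.
- The fasting point is partial, because the shared chemistry glucose is not labelled fasting either.
- Replacing the by-arm row with common-schedule events would be a poor remedy. It would drop clinically found events. The week-4 value on MK-2206 may also follow action prompted by the weekly tests, which could tilt the comparison the other way. Appendix K's data-entry schedule lists event grade, onset and resolution dates but no on-treatment glucose values.

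None of this removes the unequal looks, the expected direction of the bias or the silence of section 13.4. It does mean that a restricted comparison should be added to the full table and should not replace it.

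**Conclusion.** The point holds as an expected detection bias in a descriptive table. Because only MK-2206 patients have weekly glucose tests in cycle 1, of unstated fasting status, the by-arm summary is expected to record more hyperglycemia on that arm, chiefly mild transient cycle-1 events, even under equal true risk. With an assumed 5-20% chance of a raised value per test, the expected ratio is 1.0 to 3.7 by day 29 and 1.0 to 1.5 by week 20. The lower end applies when hyperglycemia is fully persistent and the upper end when tests are independent. No scenario examined reversed the direction, but the documents give no persistence or per-test rate, so the size cannot be fixed and an observed excess is not certain. A reader might also infer that the primary comparison or the toxicity stopping rule is compromised; neither uses this by-arm comparison.

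**What to change.** Keep the full by-arm adverse event table. Add to section 13.4:

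1. A between-arm hyperglycemia comparison limited to events detectable on the schedule common to both arms, meaning the shared 4-weekly chemistry and scheduled fasting glucose visits. Identify these events by onset date, which is already collected (the resolution date shows whether an event was still present at a shared visit), or by scheduled laboratory values where these are captured.
2. A separate listing of events found only by the extra MK-2206 cycle-1 tests.
3. A note that week-4 values on MK-2206 may follow intervention prompted by the weekly tests.

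The cost is one extra table, fewer events in the restricted comparison, and possible residual bias from earlier intervention on MK-2206. Using laboratory values in place of event dates would need data that Appendix K does not list. Monitoring and care do not change.

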1. OBJECTIVES

1.1 Primary Objectives

- 1.1.1 To assess progression free survival (PFS) of vascular endothelial growth factor (VEGF) therapy refractory renal cell carcinoma (RCC) patients who receive either MK-2206 or everolimus.
1. To assess safety of MK-2206 in patients with VEGF therapy refractory RCC

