Mild to moderate mucositis and conjunctivitis were associated with rash. The supportive-care measures included hydration, topical steroid preparations, oral corticosteroids, oral antihistamines, and oral antibiotics. Other common AEs included nausea, fatigue, vomiting, and diarrhea. These AEs were mild to moderate and in most cases were resolved by the standard supportive care and did not require therapy modifications. Hyperglycemia and hyperinsulinemia, both expected mechanism-based AEs, were observed in approximately 76% and 57% of patients, respectively, receiving MK-2206 on the QOD schedule. Episodes were generally mild, transient, and did not require therapeutic intervention. Importantly, administration of insulin may not counteract MK-2206-induced hyperglycemia due to mechanism-based insulin resistance. In this case, hydration and oral antihyperglycemic agents can be used as the supportive-care measures. Grade 3 hyperglycemia occurred in 1 patient who received 60 mg QOD and required treatment with PO antihyperglycemic medication. Grade 4 hyperglycemia was reported in one patient who received MK-2206 45 mg QOD in combination with erlotinib. In addition to supportive care measures, blood glucose management included administration of insulin and PO antihyperglycemic medication.

Grade 1/grade 2 prolongation of QTc-interval was observed in 14 out of 64 patients (21.9%) with available 12-lead ECG data. Prolongations ≥ 30 msec but < 60 msec occurred in 4 of these patients. Grade 3 QTc prolongation was reported in one patient who received 135 mg QW. Episodes of QTc interval prolongation were in general isolated with no apparent dependency on dose or exposure levels, and were not considered clinically significant by investigators and were not reported as adverse experiences. Eleven patients experienced sinus bradycardia (< 50 bpm) during Holter or ECG monitoring. These events were asymptomatic and were not clinically significant. While a causal relationship between these events and administration of MK-2206 is uncertain, similar side effects were seen preclinically in conscious dogs. Consequently, patients with a history or current evidence of heart disease should be excluded from enrollment on MK-2206 trials. Standard 12-lead ECG measurements should be performed at the protocol-specified time-points.

Developmental/Reproductive Toxicity

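### Only MK-2206 patients have a Day 1 post-dose ECG, and Section 13.4 does not set it apart, so at equal risk the by-arm summary is expected to show somewhat more isolated QTc findings on MK-2206.

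*Combined protocol and SAP*

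**What the plan says.** Section 5.2, under evaluation during treatment: "On C1D1 only, patients randomized to MK-2206 will have an ECG within 4 hours of taking study drug". Footnote j of the Section 10 calendar agrees: "Course 1 Day 1 post-treatment (only for patients randomized to MK-2206".

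The other scheduled ECGs apply to both arms:

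- Screening: a 12-lead ECG within four weeks of study entry (Section 5.2).
- On treatment: a 12-lead ECG in the block headed "In addition to the above, the following will be performed every eight weeks +/- 7 days". The interval may become 12 weeks for patients progression free after one year.
- End of treatment: a 12-lead ECG in the block headed "The following study activities will be completed after treatment has been discontinued for any reason".

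Section 5.2 also schedules "Vital signs (including weight) and ECOG performance status" every four weeks in both arms.

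On analysis, Section 13.4 says only that "safety data will be summarized by treatment arm, category, severity and relevance". It has no rule for findings that can be made in one arm only. The safety objective in Section 1.1 is "To assess safety of MK-2206 in patients with VEGF therapy refractory RCC".

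**The concern.** The chance of at least one isolated, transient finding rises with the number of ECGs read. Section 2.2 describes the QTc episodes seen so far on MK-2206 as mostly isolated and without an evident relation to dose or exposure. Of the ECG findings it says: "While a causal relationship between these events and administration of MK-2206 is uncertain". These are findings for which an additional reading in one arm matters.

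Section 2.3.3 reports no effect of everolimus on QT in preclinical work. A reader of the safety table will naturally use the everolimus column as the concurrent background rate. If one column includes a reading that the other never had, part of any gap reflects the schedule and not the drug. Safety of MK-2206 is a primary objective, so the table will be read with care.

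**Working it through.** **Figures in the documents.** They state no ECG detection rate for this trial, so there is no planned figure on this point to reproduce. The earlier-study figure in Section 2.2 checks: 14/64 = 21.9% of patients with grade 1/2 QTc prolongation. The design medians in Section 13.1 (4.9 and 8.2 months) fit the stated event count. The hazard ratio is 4.9/8.2 = 0.598, and events = (1.282 + 0.842)² / [(2/3)(1/3)(ln 0.598)²] = 77, against 75 stated. Power at 75 events is 0.794, against 0.80 stated.

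**Assumptions, not in the documents.** Time to progression is exponential. Each ECG has the same chance p of an isolated finding in both arms, independently of the patient's other ECGs. The 21.9% from earlier MK-2206 studies is taken as the rate on this trial's shared schedule.

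**Step 1: number of shared post-baseline ECGs.** These fall at weeks 8, 16, ..., 48, then every 12 weeks, plus end of treatment.

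| Median | Counting rule | Mean shared ECGs, n | Day 1 share, 1/(n+1) |
|---|---|---|---|
| 4.9 months | visit that detects progression and end of treatment counted separately | 5.1 | 16% |
| 8.2 months | same | 7.1 | 12% |
| 4.9 months | one ECG serves for both | 4.1 | 20% |
| 8.2 months | same | 6.1 | 14% |

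**Step 2: effect of one additional ECG.** Set 1 − (1 − p)^n = 0.219. With one more reading the rate is 1 − 0.781^((n+1)/n):

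- n = 5.1: p = 0.047, rate 25.6%
- n = 7.1: p = 0.034, rate 24.6%
- n = 4.1: rate 26.5%
- n = 6.1: rate 25.0%

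Letting the number of ECGs vary between patients gives 24.7% to 26.8%. Overall the excess runs from 24.6 − 21.9 = 2.7 points to 26.8 − 21.9 = 4.9 points. Times 70 patients, that is 1.9 to 3.4.

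**Step 3: other per-ECG rates.** Here the median time on treatment is 4.9 months in both arms, with a mean of about 4.0 ECGs on everolimus and 5.0 on MK-2206.

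| p per ECG | Everolimus | MK-2206 | Excess (points) | Chance that the observed rate is higher on MK-2206 (70 vs 35) |
|---|---|---|---|---|
| 1% | 3.9% | 4.9% | 1.0 | 54% |
| 2% | 7.6% | 9.5% | 1.8 | 59% |
| 5% | 17.7% | 21.8% | 4.1 | 67% |
| 10% | 31.6% | 38.4% | 6.8 | 74% |
| 20% | 51.4% | 61.1% | 9.7 | 81% |

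On identical schedules the odds are near even (at p = 5%, 47% higher on MK-2206 and 46% higher on everolimus). Up to the first 8-week ECG, the comparison is one reading against two: 5.0% against 9.8% at p = 5%. If findings fully persist and would be caught later anyway, the excess is zero.

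**Step 4: do shared ECGs alone make the comparison fair?** Not if treatment lasts longer on MK-2206. At the design medians the shared counts are 5.1 and 7.1. With everolimus at 21.9% and the same p, MK-2206 on shared ECGs only reaches 1 − 0.781^(7.1/5.1) = 29%, or 28.4% when the number of ECGs varies between patients. About 6.5 points remain with no true difference, which is more than the Day 1 reading contributes.

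**The case against.** The strongest reply is that no planned comparison is harmed. The safety objective concerns MK-2206 itself, and the by-arm summary is descriptive with no test. The stopping rule in Section 13.1 counts only Grade 3 or greater toxicity requiring discontinuation, in the MK-2206 arm alone. All of this stands and limits the importance of the point. It does not remove the point, because the summary is by arm and will be read across columns.

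The effect is also small against noise. At 21.9% with 70 and 35 patients, the standard error of the difference is √[0.219 × 0.781 × (1/70 + 1/35)] = 8.6 points, so the excess is about 0.3 to 0.6 standard errors. A reader might infer that the table is bound to show more findings on MK-2206. The documents do not support that: the excess is an expectation, and Step 3 gives 54% to 81%.

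A reader might also infer that everolimus patients have no ECG at all before week 8. In fact the window allows week 7, and a patient who stops early has an end-of-treatment ECG.

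Whether Day 1 findings reach the summary is uncertain. Section 2.2 says the earlier QTc episodes were not reported as adverse experiences, although Section 7.4 requires all adverse events to be reported.

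Nor should a higher MK-2206 rate be read as mere artefact. Section 2.2 notes similar effects in dogs, Section 3.2.7 names QTc as a possible safety concern, and Section 7.1.1 lists QTc prolongation and sinus bradycardia as possibly related to MK-2206. A Day 1 reading specific to that drug has an evident safety purpose, and nothing here argues against it.

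Finally, restricting the table to shared ECGs is not enough by itself. Step 4 shows this is right, and the fix allows for it.

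**Conclusion.** The concern holds as a minor reporting point. Followed as written, the plan is expected to raise the descriptive MK-2206 rate of isolated QTc findings, at equal risk and equal time on treatment, by about 3 to 5 percentage points (2 to 3 of 70 patients). That size rests on a 21.9% rate on the shared schedule, independence between ECGs and exponential time to progression. Across per-ECG rates of 1% to 20% the excess is 1 to 10 points. It falls toward zero if findings persist or are not recorded as adverse events.

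Bradycardia is affected only so far as it is found by ECG. It is not quantified here, because the 14/64 figure is for QTc only and bradycardia might also be noticed at the 4-weekly vital signs. PFS and the toxicity stopping rule are unaffected.

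**What to change.** Add to Section 13.4 that side-by-side summaries of QTc prolongation and ECG-detected bradycardia use only ECGs scheduled in both arms. Express them per ECG read, or up to a common time point such as the first 8-week ECG (or the end-of-treatment ECG for a patient who stops sooner), so that longer treatment in one arm does not add looks. Report Cycle 1 Day 1 findings in a separate MK-2206-only row.

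The cost is a sentence or two in the plan and one more row in the safety table. Adverse event onset dates are already collected (Appendix K data schedule), so Day 1 events can be identified even after enrolment is complete. The downside is that Day 1 events leave the comparative row, but they are still fully reported for MK-2206. The ECG schedule does not change.
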